## **1. SUMMARY OF THE STUDY**

### ***1. Type of request:***

Observational validation study of prognostic test based on clinical parameters, analytical and ultrasound.

### ***2. Identification of promoter:***

Working Group on Ultrasound of the Spanish Society of Internal Medicine (GT Eco-SEMI).

### ***3. Study title:***

"SARCO-COVID: Measurement of the loss of skeletal muscle mass in the patient hospitalized with a diagnosis of COVID-19".

### ***4. Protocol Code:***

MIR / HEEIZ\_2021\_03

### ***6. Centers in which the study is planned:***

It is a study that will be carried out at the Nurse Isabel Emergency Hospital Zandal (Madrid).

### ***7. Design:***

Observational validation study of prognostic test based on clinical parameters,

analytical and ultrasound.

#### **8. Clinical Research Ethics Committee that evaluates the study:**

Following the guidelines of the center, the study will be evaluated by the Ethics Committee of Clinical Research of the San Carlos Clinical Hospital.

#### **9. Rationale**

The COVID-19 pandemic is having a devastating global impact, and adults Older people who suffer from it have a higher risk of death from the disease. Nevertheless, survivors of the disease are at greater risk of suffering from diseases such as sarcopenia, more common in younger adults and with greater severity of disease.

Sarcopenia (from the Greek terms “*sarx*” (meat) and “*penia*” (poor quality)) today it is considered one of the most relevant syndromes, and the substrate of many of the health problems of the elderly and hospitalized patients, increasing by itself morbidity and mortality, and of course reducing activity and functional recovery. Of fact is deeply related to frailty, functional decline, falls, osteoporosis and different metabolic disorders (hydrocarbon intolerance) and homeostasis (thermoregulation) of the elderly. Sarcopenia is present in the 5-13% of people between 60 and 70 years old and in 11- 50% of the population over 80 years.

The diagnosis of sarcopenia has advanced in recent years by establishing itself in different consensuses homogeneous criteria that necessarily combine two elements: general loss of strength accompanied by loss of muscle mass skeletal. Today there are three consensuses for the diagnosis of sarcopenia: the international (IWGS), European (EWGSOP), and the most recent of a cohort American (FNIH). In all of them, the measurement of skeletal muscle mass constitutes one of the two diagnostic criteria.

The main methods to measure this muscle loss that are established are the imaging techniques (computerized tomography (CT), magnetic resonance imaging (MRI),

Dual energy X-ray absorptiometry (DEXA) and ultrasound.

The most common ultrasound measurements used for this purpose are thickness muscle (cm) at the point of the ultrasound path of maximum muscle thickness, the area of cross section (area calculated by the basic software at the point of maximum muscle thickness), and the angle of pennation (angle formed between the muscular fascia deep and muscle fibers). The first two measurements can be made in several long muscles, while the pennation angle is usually performed mainly in the

medial gastrocnemius muscle (internal twin). They are easy to obtain, bloodless and reproducible.

Research efforts at this point in the pandemic should focus on in the longer-term consequences of the disease, sequelae such as sarcopenia in patients who have suffered COVID-19. At the same time, doctors must be every time more aware of the condition and its measurement integrated into clinical practice. The knowledge that studies such as the one proposed will provide will allow the development of specific interventions.

The risk of sarcopenia should be considered when conducting an evaluation of the risk / benefit of the established treatment (for example, dexamethasone), and assess a multidisciplinary treatment that includes dietary contributions.

## ***10. Main objectives***

### ***1. Main hypothesis:***

- Patients admitted for COVID-19 present a progressive loss of mass muscle, both due to the inflammatory state, decreased intake, bedridden due to hospitalization and derivative of treatment (eg corticosteroid therapy).

### ***2. Main objective:***

- Quantify the loss of muscle mass in hospitalized patients in areas of Medicine Inmate diagnosed with COVID-19.

### ***3. Secondary objectives:***

- Analyze the clinical characteristics and prevalence of sarcopenia in patients included in the study.
- Analyze the thickness and cross-sectional area of the muscles in all patients rectus femoris, vastus medialis, vastus lateralis, medial calf and the angle of pennation of the medial twin.
- Analyze the correlation between ultrasound parameters and analytical parameters (nutritional, inflammatory).
- Determine the relationship between muscle loss and treatment received

(dexamethasone, methylprednisolone, prednisone).

- Determine the relationship between muscle loss and days of hospitalization or severity of illness.

### ***11. Study population and total number of patients***

Patients over 18 years of age who are admitted to the hospital and whose primary diagnosis and reason for staying is COVID-19 pneumonia. The prevalence of sarcopenia in hospitalized patients is 15-20%. Assuming a alpha risk of 0.05 and beta risk of 0.2 in a one-sided contrast, 64 subjects are required to detect a difference equal to or greater than 20% loss of muscle mass. It has been an estimated loss to follow-up rate of 0%.

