#### *b. Definition of study population*

Patients over 18 years of age who are admitted to the hospital and whose primary diagnosis and reason for staying is COVID-19 pneumonia. For a 95% confidence interval, with a precision level of 3%, an estimated loss in

about 3% of muscle mass in COVID-19 patients for an admission less than 10 days, we hope to recruit 124 patients. A loss to follow-up rate has been estimated 0%.

Subjects will be followed up during hospitalization and one month after the time of recruitment. The 30-day follow-up will be done by reviewing the history clinic, and a telephone contact would be made.

After signing the Informed Consent, the parameters included in the Data Collection Notebook, included in Annex I.

All examinations will be labeled by a unique code, the history number clinic and archived in digital format.

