#### *c. Inclusion and exclusion criteria.*

Patients who meet the following criteria will be included:

- Over 18 years old, men or women.
- Main diagnosis is pneumonia due to COVID-19

- Subjects who, after having received the information on the design, the purposes of the project, the possible risks that may arise from it and that in any moment they can deny their collaboration, verbally grant their consent to participate in the study.

The exclusion criteria to participate in the study are:

- Refusal of the patient to participate in the study.
- Present a malignant neoplasm in active phase except Ca spino- or basal cell in local stage
- Clinical situation of agony.
- Amputation of limb (s).

*d. Origin of the data:*

The data will be collected prospectively.

*and. Schedule and expected date of completion:*

The study will begin in **February 2021**, with an estimated duration of **3 months** (1 month for application, 1 month for data collection, 1 month for results analysis and preparation of articles and / or communications).

*and. Sample size:*

Patients over 18 years of age who are admitted to the hospital and whose primary diagnosis and reason for staying is COVID-19 pneumonia. For a 95% confidence interval, with a precision level of 3%, an estimated loss in about 3% of muscle mass in COVID-19 patients for an admission less than 10 days, we hope to recruit 124 patients. A loss to follow-up rate has been estimated 0%.

Subjects will be followed up during hospitalization and one month after consultation. recruitment. The 30-day follow-up will be done by reviewing the history

clinic, and a telephone contact will be made.

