#### **Four. V ARIABLES IN EVALUATION**

Data to collect:

\* PRIMARY VARIABLE:

*to. Variables related to ultrasound:*

To collect these variables, the GE VENUE will be used, the linear probe will be used (5.5–7.5 MHz) (General Electrics Healthcare, Madrid, Spain).

All patients will undergo a muscle ultrasound upon admission to the center and prior to upon discharge, using the usual muscle sweep technique. The ultrasound will be performed on the rectus femoris, vastus medialis, vastus lateralis and medial calf muscles. They will be measured:

- Muscle thickness in its cross section (in mm), in the plane of maximum thickness

in longitudinal sweep

- Cross-sectional area (in  $\text{cm}^2$ ) in the plane of maximum area in the scan longitudinal
- Angle of penetration (in degrees) of the medial twin, using the base of the angle the deep muscle fascia and as an angle the maximum inclination of the you muscle mass.

This exam will be carried out by 5 experienced physicians according to the criteria of the ACEP (American College of Emergency Physicians) and who carry out more than 10 studies ultrasounds per week and at least 3 years of experience in the performance and interpretation of ultrasound examinations. A reliability study will not be conducted given the limitation in the time and current healthcare pressure.

In addition, to avoid the possible bias that inter-operator variability would suppose in these circumstances, the research team was provided with a training program and designed internal training consisting of:

- Theoretical course on basic, systematic musculoskeletal ultrasound, medication, etc.
- Practical seminars in which an ultrasound machine and healthy models will be used to your measurement.
- Supervised practical training with real hospital patients until assessing an adequate measurement of at least 5 patients.
- The team of 5 doctors adequately trained in this technique were specific to this trial to avoid protocol deviations and any other form of interoperator variability.

\* SECONDARY VARIABLES:

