### **PROCEDURE FOR CLEANING THE MATERIAL ECOGRAPHY**

The ultrasound machine will be at all times in the consultation reserved for attention to suspected COVID.

Before carrying out: hand washing with soap and water. Will wash first with enzymatic detergent (optional) and then with alcohol 96% all the surface of the ultrasound system including cable and ultrasound support area, except for the probe. The tube will be cleaned with Clinell®.

During the procedure: the examination will be done with the “dirty” hand in contact with the patient avoiding touching the rest of the ultrasound machine to the extent the possible. The other hand (“clean”) will be left to handle the ultrasound machine (amplitude, gain, zoom, ...).

After completion: it will be washed again with 96% alcohol. Washing hands.

Wait at least until the ultrasound machine has dried after the disinfection procedure before restarting the process.

*c. Practical considerations:*

INCLUSION PHASE:

All patients admitted to HEEIZ hospital will be selected. I know will verify that they meet the inclusion criteria and none of the exclusion criteria, and they will be informed of the objectives and procedures of the study, giving them the information sheet and requesting their verbal informed consent. CRF

COMPLIANCE:

The diagnostic and therapeutic management of the patient will be carried out according to clinical practice usual, filling in the CRF all demographic variables, physical examination, diagnostic, ultrasound and follow-up variables that appear in section 4 of this protocol.

FOLLOW-UP OF PATIENTS:

Patients will be followed up to day 30 after inclusion in this study (well, after hospital discharge or until the day of death if it occurs before day 30), in order to evaluate the main variables. The follow-up will be done by reviewing the electronic medical record, and will be contacted by phone.

ANALYSIS OF RESULTS:

Once the follow-up of the last patient has been completed, the statistical analysis of the results and the final study report will be prepared.

FINANCING:

This is an unfunded study sponsored by researchers. The promoter (Group of GTEco-SEMI ultrasound) will provide the necessary material (information, notebook, methodology and logistics) to carry out the study.

*d. Schedule:*

The total duration of the project is estimated at **03 months** .

	FEBRUARY	MARCH	APRIL	APRIL
Authorization request by the CEIC and classification by AEMPS	•			
Identification of patients		•		

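### The summary asks for 64 subjects and the body for 124; nothing reconciles them, and neither number rests on the variability of a within-patient muscle change

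*Combined protocol and SAP*

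**What the plan says.** Summary item 11, whose heading covers the total number of patients, states that "64 subjects are required to detect a difference equal to or greater than 20% loss of muscle mass". The inputs are a one-sided contrast, alpha 0.05 and beta 0.2. A sarcopenia prevalence of 15-20% is mentioned just before, but is not said to enter the calculation. The item closes with "It has been an estimated loss to follow-up rate of 0" per cent.

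Section 3.b and the sample-size paragraph of section 3 give a different basis: "For a 95% confidence interval, with a precision level of 3%, an estimated loss in about 3% of muscle mass in COVID-19 patients", tied to stays shorter than 10 days, and then "we hope to recruit 124 patients". The sample-size paragraph adds "A loss to follow-up rate has been estimated 0" per cent.

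The main objective (summary item 10, repeated in section 2.g) is to "Quantify the loss of muscle mass in hospitalized patients". Section 4 makes the ultrasound measurements the primary variable: "All patients will undergo a muscle ultrasound upon admission to the center", with a second scan before discharge. The statistical analysis paragraph of section 5 names the standard deviation only as a descriptive summary and leaves missing values missing. Section 5.c follows patients to day 30, or "until the day of death if it occurs before day 30". The Annex I data form has entries for loss to follow-up and for mortality.

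**The concern.** The two statements differ in three ways: the number (64 or 124), the framework (a powered one-sided test or an interval of given precision) and the assumed effect (a loss of at least 20% or of about 3%). Both stand in current text and neither refers to the other. A reader of the summary and a reader of section 3 would therefore approve different studies.

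The second problem is the basis of the numbers. With a scan at admission and another before discharge in the same patient, the natural estimate for the main objective is the mean within-patient change in a continuous measure. Its precision depends on the SD of that change and on the number of patients with both scans. The plan gives no SD and assumes that every patient has both scans. The claims of 80% power and 3% precision therefore do not follow from anything in the plan, and the precision of the main result cannot be worked out from it.

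**Working it through.** **Inputs from the documents.** Summary item 11: n = 64, one-sided alpha 0.05, power 80%, 20% loss, 0% attrition. Section 3: n = 124, 95% interval, precision 3%, expected loss 3%, 0% attrition. SD of change: not given, so SDs of 5, 10 and 20 percentage points are assumed below to show a range.

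**Reproducing 124.** The sample size for a single proportion is n = 1.96² × p(1 − p) / d². With p = 0.03 and d = 0.03, n = 3.8416 × 0.0291 / 0.0009 = 124.2. The figure reproduces, but as the number needed to estimate that 3% *of patients* have some feature. A mean loss of 3% of muscle is a different quantity, and p(1 − p) is not its variance.

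**Reproducing 64.** The plan does not state the origin. One calculation that matches is two independent proportions, 20% against 40%, pooled variance, one-sided 0.05, 80% power:

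[1.645 × √(2 × 0.3 × 0.7) + 0.842 × √(0.2 × 0.8 + 0.4 × 0.6)]² / 0.2² = 63.9 per group.

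The 40% is my inference. Starting from 15% or 17.5% with the same 20-point difference gives 57 or 61 per group. If this is the source, it belongs to a two-group design, and this study has one cohort.

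**What 64 would mean for a paired mean.** The normal approximation is n = (1.645 + 0.842)² × (SD / 20)². Setting n = 64 gives SD = 20 × √(64 / 6.18) = 64 points; the noncentral t distribution gives 63.7. Power at n = 64 is 0.99 at SD 40 and 0.84 at SD 60. So 64 is not shown to be too few for a 20-point mean loss. The 80% figure simply has no stated basis.

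**Precision of a mean change.** The 95% half-width is t(0.975, n − 1) × SD / √n. The SD limit is the SD at which the half-width equals 3 points.

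| Patients with both scans | SD 5 | SD 10 | SD 20 | SD limit |
|---|---|---|---|---|
| 64 | 1.25 | 2.50 | 5.00 | 12.0 |
| 124 | 0.89 | 1.78 | 3.56 | 16.9 |
| 111 (124 less an assumed 10%) | 0.94 | 1.88 | 3.76 | 15.9 |
| 99 (124 less an assumed 20%) | 1.00 | 1.99 | 3.99 | 15.0 |

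Whatever the SD, the interval at 64 is 2.50 / 1.78 = 1.4 times as wide as at 124.

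**The case against.** The best reply is that the body governs. It states 124 twice, once in the paragraph devoted to sample size, and the other text is only a summary. Recruiting 124 would also satisfy a requirement for 64. That makes 124 the likely intention, but no rule of precedence is written, and the two texts still assume effects of 20% and about 3%.

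A second reply is that the 3% figure is qualified by stays shorter than 10 days, so the two effects may describe different patients. The qualifier describes the expected loss. It supplies no variability, and the plan does not use it to connect the two calculations.

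Third, the plan never defines its estimate as a mean within-patient percent change; it allows medians and lists several muscles and measures as primary. This is fair: the mean paired change is a reading of the objective together with the two scans. It is the natural reading, and neither calculation fits any other version of a continuous loss better.

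Fourth, much of the attrition evidence concerns the 30-day follow-up by records and telephone, which costs no scan. That stands. Only death or a missed scan before discharge removes a pair, and the 10% and 20% used above are assumptions.

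Finally, neither size is shown to be too small. That also stands, and no such claim is made here.

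**Conclusion.** The point holds. Current text carries two sample sizes, 60 patients apart, built on different frameworks and different assumed effects, with nothing to reconcile them. Neither is justified for a mean within-patient change. The 124 comes exactly from a formula for a proportion, and the basis of 64 is not stated. This conclusion needs no assumption about the SD.

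How much precision is at stake does depend on the SD: the 3% claim is met at 124 only up to about 16.9 points, and that limit falls to 15.9 or 15.0 if 10% or 20% of patients have no second scan. The assumption of no loss is optimistic for a plan that provides for deaths and leaves missing values missing, but the true share without a second scan is unknown.

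**What to change.** 1. Remove the 64-subject calculation and its power statement from summary item 11, and give one N there, in section 3.b and in the sample-size paragraph of section 3.
2. Keep 124 if wished, but replace the proportion-based justification with the precision of the mean within-patient percent change, admission to pre-discharge, in one named ultrasound measure.
3. Give the 95% half-width over a range of SDs (about 0.9, 1.8 and 3.6 points at SDs of 5, 10 and 20). State that 3-point precision holds only if the SD is at most about 16.9. If a sourced SD of change is available, cite it and mark it in the range.
4. State that these figures count patients with both scans. Replace the 0% loss in all three places with an assumed share without a second scan, and show the half-widths for the resulting pairs (for example 111 at 10% or 99 at 20%).

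The cost is rewording in three places. No extra enrolment is needed if 124 is kept. The sponsor gives up the unqualified 80% power and 3% precision claims, and must name one measure and state its assumptions about the SD and missing second scans.

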### ***12. Schedule and expected date of completion***

The study will begin in **February 2021** , with an **estimated duration of 3 months** (1 month for application, 1 month for data collection, 1 month for results analysis and preparation of articles and / or communications).

## 2. GENERAL INFORMATION

*to. Project identification.*

**Protocol code:** MIR / HEEIZ\_2021\_03

**Promoter:** Working Group on Ultrasound of the Spanish Society of Internal Medicine (GT Eco-SEMI).

**Qualification:**

"SARCO-COVID: Measurement of the loss of skeletal muscle mass in the patient hospitalized with a diagnosis of COVID-19".

*b. Principal researchers. Work center address:*

[name] [name] and [name] [name].

University Hospital of Emergencies Nurse Isabel Zandal.

[name]

*c. Research Center.*

Hospital de Emergencias Nurse Isabel Zandal.

*d. Ethical Committee for Clinical Research.*

Following the guidelines of the center, the study will be evaluated by the Ethics Committee of

Clinical Research of the Hospital Clínica San Carlos, whose composition is already known accredited by the Ministry of Health. The study will be evaluated by the CEIC of each hospital where the study will be performed.

*and. Expected duration of the project.*

The study will begin in **February 2021**, with an **estimated duration of 3 months** (1 month for application, 1 month for data collection, 1 month for results analysis and preparation of articles and / or communications). The estimated timetable for the development of the study:

**Presentation to CEIC: February 2021.**

**Data collection: March 2021.**

**Analysis of results: April 2021**

**Preparation of articles, communications: April 2021.**

*F. Reason for the project.*

The COVID-19 pandemic is having a devastating global impact, and adults Older people who suffer from it have a higher risk of death from the disease. Nevertheless, survivors of the disease are at greater risk of suffering from diseases such as sarcopenia, more common in younger adults and with greater severity of disease.

Sarcopenia (from the Greek terms “*sarx*” (meat) and “*penia*” (poor quality)) today it is considered one of the most relevant syndromes, and the substrate of many of the health problems of the elderly and hospitalized patients, increasing by itself morbidity and mortality, and of course reducing activity and functional recovery. Of fact is deeply related to frailty, functional decline, falls, osteoporosis and different metabolic disorders (hydrocarbon intolerance) and homeostasis (thermoregulation) of the elderly. Sarcopenia is present in the 5-13% of people between 60 and 70 years old and in 11- 50% of the population over 80 years.

The diagnosis of sarcopenia has advanced in recent years by establishing itself in different consensus homogeneous criteria that necessarily combine two elements: general loss of strength accompanied by loss of muscle mass skeletal. Today there are three consensus for the diagnosis of sarcopenia: the international (IWGS), European (EWGSOP), and the most recent of a cohort American (FNIH). In all of them, the measurement of skeletal muscle mass constitutes one of the two diagnostic criteria.

The main methods to measure this muscle loss that are established are the imaging techniques (computerized tomography (CT), magnetic resonance imaging (MRI), Dual energy X-ray absorptiometry (DEXA) and ultrasound.

The most common ultrasound measurements used for this purpose are thickness muscle (cm) at the point of the ultrasound path of maximum muscle thickness, the area of

cross section (area calculated by the basic software at the point of maximum muscle thickness), and the angle of pennation (angle formed between the muscular fascia deep and muscle fibers). The first two measurements can be made in several long muscles, while the pennation angle is usually performed mainly in the medial gastrocnemius muscle (internal twin). They are easy to obtain, bloodless and reproducible.

Research efforts at this point in the pandemic should focus on in the longer-term consequences of the disease, sequelae such as sarcopenia in patients who have suffered COVID-19. At the same time, doctors must be every time more aware of the condition and its measurement integrated into clinical practice. The knowledge that studies such as the one proposed will provide will allow the development of specific interventions.

The risk of sarcopenia should be considered when conducting an evaluation of the risk / benefit of the established treatment (for example, dexamethasone), and assess a multidisciplinary treatment that includes dietary contributions.

*g. Objectives of the study.*

